8.3 Overall Survival

Overall survival (OS) probabilities will be calculated using Kaplan-Meier methodology. Overall survival will be defined as the time from the “start date” of first RGI-2001 infusion to the date of death due to any cause. Death date will be obtained from *Discontinuation* eCRF. Censoring: Subjects who are known to have not died are censored at the date last known to be alive (usually EOS visit date), with follow-up truncated at one year (365 days). There are no competing risk events. Kaplan-Meier estimates of this endpoint as a function of time will be provide for visual purposes.

8.4 Disease-Free Survival (DFS)

DFS rates (synonymous with Relapse-Free Survival [RFS]) will be calculated using Kaplan-Meier methodology. For each subject, DFS will be calculated as time from the “start date” of first RGI-2001 infusion to relapse, disease progression, or death from any cause, whichever occurs first. Censoring: Subjects who do not experience any DFS events will be censored on the last evaluation of relapse/progression (using the *Disease Status Follow-up* eCRF), with follow-up not extending beyond one year. There are no competing risk events. Kaplan-Meier estimates of this endpoint as a function of time will be provide for visual purposes.

Date of first relapse will be obtained using the *Disease Status Follow-up* eCRF where Question 7 “Disease Status” = “1st relapse” or “Relapse from complete remission”. This eCRF contains three dates: Question 1 Date of Bone Marrow Aspirate, Question 2 Date of Bone Marrow Biopsy, and Visit Date. If multiple dates are provided, the first will be used to define the Date of First Relapse.

Date of first progression will be obtained using the *Disease Status Follow-up* eCRF where Question 7 “Disease Status” = “Progression from hematologic improvement”. Similar to relapse, the first of the three dates will be used to define the Date of First Progression.

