## 7 SUBJECT POPULATION

### 7.1 Inclusion Criteria

All subjects (including CIBMTR control group, except where noted) must meet the following criteria:

1. Ages  $> 18$  and  $\leq 65$  years of age
2. Has a hematologic malignancy as defined below and is considered a candidate for allo HSCT:
  - a. Acute myelogenous leukemia (AML) in first or subsequent morphologic complete remission
  - b. T or B cell acute lymphoblastic leukemia (ALL) in first or subsequent complete morphologic remission
  - c. Myelodysplastic syndrome (MDS), chronic myelomonocytic leukemia (CMML), myeloproliferative disorder (MPD) including myeloid metaplasia and myelofibrosis and are currently with  $< 10\%$  blasts in bone marrow
  - d. CML subjects who have received prior treatment including at least one tyrosine kinase inhibitor and are currently in chronic phase or with a complete hematologic remission but with evidence of cytogenetic or molecular relapse
3. Must have adequate organ function as defined below (RGI-2001 treatment group only):
  - a. Cardiac function: Left ventricular ejection fraction at rest  $\geq 45\%$
  - b. Liver function: total bilirubin  $< 1.5$  x upper limit of normal (ULN); alanine aminotransferase (ALT) and aspartate aminotransferase (AST)  $< 2.5$  x the ULN. Patients who have been diagnosed with Gilbert's Disease or malignant involvement are allowed to exceed the defined bilirubin value of  $1.5$  x the ULN
  - c. Serum creatinine  $< 2$  mg/dL or estimated creatinine clearance  $> 50$  mL/min calculated using the Cockcroft-Gault equation
  - d. Pulmonary: DLCO (corrected for hemoglobin) and/or FEV1  $\geq 50\%$
4. Considered suitable candidate for a myeloablative allogeneic or unrelated donor transplant based on institutional criteria
5. Subject must be receiving first allogeneic transplant from a single donor. Prior autologous transplant is acceptable
6. Transplant Donor:
  - a. Matched related donor (8/8): Molecular identity at HLA-A, -B, -C and -DRB1 by high-resolution typing
  - b. Unrelated donor ( $\geq 7/8$  allelic match): high resolution molecular typing at the following loci is required HLA -A, -B, -C and -DRB1
  - c. Meets institutional criteria for bone marrow or PBSC donation (see [Section 7.4](#))

7. Source of the Allograft:
  - a. Unmodified bone marrow or mobilized peripheral blood stem cell (PBSC) transplant, using granulocyte colony stimulating factor (G-CSF) as the mobilizing agent. Cord blood is not allowed

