4.0 STATISTICAL METHODS OF ANALYSIS

4.1 Statistical Considerations

Continuous variables will be summarized (based on the subjects with non-missing values) by the number of subjects (n), mean, standard deviation (SD), median, minimum value, and maximum value. Mean and median will be accurate to one more digit decimal point than the original data, and standard deviation will be accurate to two more-digit decimal points than the original data, and the decimal points of the maximum and minimum values will be the same as the original data.

Categorical variables will be summarized (based on the subjects with non-missing values) by the frequency (count and percent) of subjects falling within the category. The denominator for all

percentages, unless otherwise specified, will be the number of subjects in the specified analysis population.

Point estimates of time-to-event outcomes will be obtained using either Kaplan-Meier or cumulative incidence estimates, depending on whether endpoints have competing risks. Survival at a variety of specific endpoints will be presented in the tabled output, including Day 100 (i.e., primary endpoint for aGvHD) and Day 365 (i.e., EOS). In addition (if applicable), the median length of survival (in days) will be presented. Furthermore, listed data for all time-to-event outcomes will be provided.

Regarding the time-to-event estimates, the time between begin and end dates for events and censors is important in the calculation. If either of the dates are invalid, then the 1st will be assumed (for missing day) and/or January will be assumed (for missing month). Assumptions will only be incorporated into the analysis if calculation of time does not result in a negative number of days. If negative, the subject will not be used in the analysis. If assumptions are needed, they will be flagged in the listings.

Almost all data from the electronic case report form (eCRF) will be listed. For example, time (mm:hh) will be excluded from almost all listings except for the PK and PD listings. From lab listings, the lab name and the original value for the dose in the units collected on the eCRF will be excluded and replaced with the value in SI units. Also a few variables collected on the AE eCRF and other eCRFs will be excluded from the listings.

Baseline will be defined as the last assessment completed prior to the administration of the study drug (Day 0, which corresponds with date of transplant).

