8.5 Non-Relapse Mortality (NRM)

Non-relapse mortality (NRM) rates will be calculated using a cumulative incidence estimate for visual purposes. NRM will be defined as the occurrence of death without prior relapse, with relapse a competing risk for NRM. For each subject, time to death will be calculated as described in the above OS section and time to relapse will be calculated as described in the DFS section.

Event and censoring assignments will proceed as follows:

- Subjects with no relapse and no death will be censored at the last time known to be alive.
- Subjects with no relapse who die will be counted as events.
- Subjects with relapse will be considered a competing risk at the time of first relapse.
- Follow-up will not extend beyond one year.

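### SAP 8.5 competes NRM on relapse alone, so a death after coded progression without recorded relapse counts as non-relapse mortality

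*SAP*

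**What the plan says.** SAP 8.4 defines DFS as time to "relapse, disease progression, or death from any cause, whichever occurs first". Both disease dates come from Question 7 of the Disease Status Follow-up eCRF, through different answers. The relapse date uses two relapse codes. The progression date uses "Progression from hematologic improvement". These are two derived variables.

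SAP 8.5 then states: "NRM will be defined as the occurrence of death without prior relapse, with relapse a competing risk for NRM". Its event rule is "Subjects with no relapse who die will be counted as events". It takes time to relapse from the DFS section and never mentions progression.

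Two other places bear on this:
- Protocol Section 5 lists NRM at Day 100, 6 months and 1 year as a secondary endpoint. Its footnote on GRFS names relapse and progression together, as does SAP 8.7.
- Protocol 7.1 requires AML and ALL subjects to be in complete remission. It also admits "Myelodysplastic syndrome (MDS), chronic myelomonocytic leukemia (CMML), myeloproliferative disorder (MPD) including myeloid metaplasia and myelofibrosis", for whom the requirement is fewer than 10% marrow blasts.

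**The concern.** NRM is meant to isolate deaths that are not due to the malignancy. A subject whose disease has progressed has already failed from disease, and 8.4 agrees by ending disease-free time there. Under 8.5 the same subject stays at risk for NRM after progression, and a later death is counted as non-relapse mortality. The error runs one way, since the rule can only add deaths to NRM.

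AML and ALL subjects enter in remission, so their disease failures would ordinarily be coded as relapse. The exposed group is mainly MDS, CMML and MPD, where the progression code can apply without a relapse code. What is at stake is a named secondary endpoint that may attribute disease deaths to the transplant or the drug.

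**Working it through.** The plan states no figure on this point to reproduce. The check follows one subject through both rules, then does the arithmetic. The only documentary input is n = 50 treated subjects (SAP 2.3). All event counts and rates below are assumed.

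**One subject under each rule.** Take an MDS subject coded as progressed on Day 150, never coded as relapsed, who dies on Day 250.
- 8.4: DFS event on Day 150, from progression.
- 8.5: no relapse, so no competing event on Day 150. The death on Day 250 is an NRM event.
- With progression as a competing event: removed from NRM on Day 150, and no NRM event.

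**Size with complete follow-up.** Let a be deaths without relapse or progression, and b deaths after progression with no recorded relapse.
- NRM under 8.5 = (a + b)/n.
- NRM with progression competing = a/n.
- Inflation = b/n, which is 1/50 = 2 points per such death.

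**Example.** Assume 8 relapses, 2 progressions followed by death, 1 progression still alive, and 5 deaths without either (a = 5, b = 2).
- DFS = 1 − (8 + 2 + 1 + 5)/50 = 34/50 = 68%.
- Relapse or progression = (8 + 2 + 1)/50 = 22%.
- NRM under 8.5 = 7/50 = 14%; with progression competing, 5/50 = 10%.
- Consistency: 68 + 22 + 10 = 100, whereas 68 + 22 + 14 = 104. The extra 4 points are the two deaths counted both as disease failures and as NRM.

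**Range.** Write b = 50 × (share with MDS/CMML/MPD) × (proportion of them progressing without recorded relapse) × (proportion of those dying within the year).
- 50 × 0.20 × 0.10 × 0.5 = 0.5 deaths, or 1 point.
- 50 × 0.30 × 0.20 × 0.5 = 1.5 deaths, or 3 points.
- 50 × 0.40 × 0.30 × 0.5 = 3.0 deaths, or 6 points. This case multiplies three high guesses and is an upper end.
- If every progression is also coded as relapse, b = 0 and there is no error.

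**With dropout.** I used 1,000 simulated trials per setting, n = 50, with constant yearly hazards: relapse or progression 0.25, death without either 0.12, dropout 0.15, and death after relapse or progression 2.0. Censoring was the same for both definitions. Mean 1-year NRM, progression competing versus 8.5 as written:
- no events coded only as progression: 10.2% versus 10.2%
- 10% of disease events coded only as progression: 10.1% versus 11.3%
- 25% so coded: 10.5% versus 13.5%

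**Precision of the optional addition.** The half-width of a 95% interval is 1.96 × √(p(1 − p)/50). For p = 15%, 25% and 35% this gives ±9.9, ±12.0 and ±13.2 points.

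**The case against.** The best defence is that 8.5 takes time to relapse from the DFS section, and that section treats DFS and relapse-free survival as the same thing while including progression. On that reading, relapse in 8.5 already covers progression. The text does not carry it: 8.4 derives a relapse date and a progression date separately, and 8.5 calls on relapse only. At best the wording is ambiguous, and two programmers could produce different NRM curves from the same data.

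The second defence is size. The rates are assumed, the error may be zero, and a few points are small against a sampling half-width of ±9.9 points at a 15% rate with n = 50. Day 100 is little exposed, because the first scheduled post-transplant marrow is near Day 100. All of this stands. It limits the importance of the point but does not justify a rule that biases in one direction and costs almost nothing to correct.

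A reader might also infer several stronger things, which the documents do not support.
- **That the trial will not report relapse incidence.** No readable part of SAP Section 8, nor its table and figure lists, plans it. But exploratory endpoints are blacked out, table shells are separate, and the CIBMTR comparison has its own SAP, which was not supplied. Listings of outcome dates are also planned.
- **That relapse must be recovered as 1 − DFS − NRM, with a faulty interval.** No document proposes that subtraction. SAP 4.1 says "Point estimates of time-to-event outcomes will be obtained using either Kaplan-Meier or cumulative incidence estimates" and the SAP names no confidence interval for any endpoint, so that gap is not specific to relapse.
- **That the censoring rules do serious damage.** DFS subjects without an event "will be censored on the last evaluation of relapse/progression", while for NRM "Subjects with no relapse and no death will be censored at the last time known to be alive". Tumor assessments are scheduled at Day 365 and at early termination, so the dates should usually be close. In the simulation this difference alone moved implied relapse by about 0.2 points.
- **That RGI-2001 raises relapse.** The protocol does not say so; its evidence that graft-versus-leukemia effects are spared is preclinical.

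**Conclusion.** The concern holds for the NRM definition. SAP 8.5 as written counts deaths after progression without recorded relapse as non-relapse mortality, which is inconsistent with 8.4 and inflates a named secondary endpoint. That reading rests on the text alone. The size does not: it is zero if every progression is also coded as relapse, 4 points in the two-death example, and 1 to 6 points over the assumed range, with the top of that range unlikely. The 6-month and 1-year figures are more exposed than Day 100. The finding does not extend to DFS censoring, or to a claim that relapse goes unreported.

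**What to change.** In SAP 8.5, define NRM as death without prior relapse or progression. Make the earlier of first relapse and first progression, using the 8.4 dates, the competing event, and amend the event and censoring bullets to match. This is a wording change; both dates are already derived and no new data are needed.

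Optional, unless the redacted endpoints or the separate CIBMTR SAP already provide it: report the cumulative incidence of relapse/progression at 6 months and 1 year with a 95% CI beside NRM, with death without either as the competing event. The cost is one table and one figure. At n = 50 the interval is roughly ±10 to 13 points, so the result is descriptive, and an unremarkable estimate should not be read as reassurance. DFS censoring can stay as it is.

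### The relapse and progression codes in SAP 8.4 miss progression from stable MDS/CMML/MPD and CML leaving chronic phase, and SAP 8.5 counts deaths after progression as NRM

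*SAP*

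**What the plan says.** SAP 8.4 defines DFS as the time from first "infusion to relapse, disease progression, or death from any cause, whichever occurs first". It then reduces the two disease components to specific form answers. Relapse is dated from the Disease Status Follow-up eCRF where "Question 7 “Disease Status” = “1st relapse” or “Relapse from complete remission". Progression is dated from the same form where "Question 7 “Disease Status” = “Progression from hematologic improvement". No other answer, form or cause of death is used. A subject with no event "will be censored on the last evaluation of relapse/progression".

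SAP 8.5 takes the relapse time from the DFS section and states that "NRM will be defined as the occurrence of death without prior relapse, with relapse a competing risk for NRM". It adds that "Subjects with no relapse who die will be counted as events". Progression is not mentioned in 8.5. SAP 8.7 (GRFS) reuses the relapse and progression definitions given above it.

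Protocol 7.1 sets the population these codes must cover:
- "Acute myelogenous leukemia (AML) in first or subsequent morphologic complete remission", with a parallel rule for ALL.
- MDS, CMML and MPD with marrow blasts below 10%. Neither remission nor hematologic improvement is required.
- "CML subjects who have received prior treatment including at least one tyrosine kinase inhibitor and are currently in chronic phase", or in complete hematologic remission with cytogenetic or molecular relapse.

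**The concern.** The DFS definition is general, but the rule that implements it is a closed list of three answers. If an eligible subject's disease can fail in a way that none of the three describes, a programmer following the SAP will not record the failure. DFS, GRFS and NRM are all secondary endpoints, and all depend on this rule.

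There is also an inconsistency between 8.4 and 8.5. DFS treats progression as failure of disease control, while NRM treats only relapse that way. A death from progressing disease is then reported as non-relapse mortality, the quantity a reader uses to judge harm from the transplant and from RGI-2001. The adverse event tables are a weak backstop, because Protocol 10.4 keeps disease progression, including fatal progression, out of SAE reporting.

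**Working it through.** The plan gives no figure on this point to reproduce. The check sets the accepted answers against the eligible disease states and follows the result through the endpoint rules.

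**Step 1. Is there an accepted answer?**

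| Entry state (Protocol 7.1) | Failure after transplant | Accepted answer in SAP 8.4 |
|---|---|---|
| AML/ALL, first or later remission | Relapse from that remission | Yes, on a literal reading of the second relapse answer |
| MDS/CMML/MPD, blast limit only | Relapse after a complete remission | Yes |
| MDS/CMML/MPD, blast limit only | Progression after hematologic improvement | Yes |
| MDS/CMML/MPD, blast limit only | Progression from stable or non-responding disease | None |
| CML in chronic phase | Moves out of chronic phase | None |
| CML in hematologic remission | Hematologic relapse | Arguably the second relapse answer |
| Any | Cytogenetic or molecular relapse only | No stated rule |

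The clear gap is the two rows marked None.

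**Step 2. What do the endpoint rules then do?**

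| Course | DFS | GRFS | NRM |
|---|---|---|---|
| Failure not captured, alive at one year | Event lost; censored | Event lost unless a GvHD event occurs | Censored as alive |
| Failure not captured, dies within the year | Event dated at death | Event dated at death, or at a GvHD event if earlier | Counted as NRM |
| Progression captured, then dies | Event dated correctly | Event dated correctly | Still counted as NRM |

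Late dating is not always harmless. DFS and GRFS are also reported at 6 months, so an uncaptured failure before 6 months with death after it leaves the subject event-free at that time point.

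The last row does not depend on the form at all. It follows from 8.5 naming relapse alone. Adding progression codes to 8.4 would therefore not correct NRM.

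**Step 3. Size.** SAP 2.3 plans 50 treated subjects. One misclassified death moves crude NRM by 1/50 = 2 percentage points, two by 2/50 = 4, and three by 3/50 = 6. One lost DFS event likewise moves crude one-year DFS by 2 points. For scale, Protocol 12.4 calls a true Day-100 NRM rate of 10% or more excessive.

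The number of such subjects is not in the documents. As an illustration only, assume 10% to 50% of subjects are open to such a failure and 5% to 20% of those die after it:
- low: 50 × 0.10 × 0.05 = 0.25 deaths, and 0.25/50 = 0.5 points
- high: 50 × 0.50 × 0.20 = 5 deaths, and 5/50 = 10 points

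Both inputs are assumptions, and the width of the range shows that no single figure can be defended.

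**The case against.** The strongest objection is that the full list of Question 7 answers is not in the documents. Protocol 9.3.1 (Tumor Assessment) appears in the table of contents, but its text is not in the copy available, so a definition there cannot be excluded. SAP 3.0 shows that the plan was written with some knowledge of study data, and the three answers may simply be the ones that occurred. The comparison with CIBMTR controls is in a separate SAP, so this one describes a single arm. Disease status and outcome dates are listed by subject (Listings 16.2.21, 16.2.22 and 16.2.33), so an unmapped event could be seen.

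These points limit the size of the problem. They do not remove it: the SAP states a closed rule, does not say that the answers exhaust the form or the data, and a listing does not change an endpoint derivation. The omission of progression from 8.5 is untouched by any of them.

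Several stronger readings are tempting and are not supported:
- **All relapses from a second or later remission are missed.** The numbered first-relapse answer might suggest separate later-numbered answers. Read literally, the other relapse answer covers relapse from any complete remission. The first-relapse label could also mean the first relapse after transplant, since pre-transplant history has its own eCRF (SAP 6.3). These relapses are lost only if the form uses later-numbered answers, which the documents do not show.
- **All CML relapses are missed.** Relapse from hematologic remission may be captured. CML may also be uncommon here; it is not named among the diagnosis categories for adjustment in Protocol 12.3.1.
- **DFS and GRFS are wrong for every missed subject.** Death is itself an event, so a subject who dies within the year still has one, dated late.
- **The Day-100 NRM suspension rule is distorted.** Nothing says that the safety review committee's count uses the SAP derivation.

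**Conclusion.** The concern holds in a limited form. As worded, SAP 8.4 has no accepted answer for progression from stable or non-responding MDS/CMML/MPD, or for CML leaving chronic phase, although Protocol 7.1 admits these subjects. The event is lost from DFS in those alive at one year, and from GRFS if they also have no GvHD event; otherwise it is dated late. Independently, SAP 8.5 counts death after progression as NRM whether or not 8.4 records the progression.

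Each misclassified death is worth about 2 points of crude NRM with 50 subjects. The total cannot be derived from the documents and could be zero if no such subject was enrolled. The first part of the conclusion rests on the SAP wording being applied as written and on no overriding definition in Protocol 9.3.1. The second part rests on the text of 8.5 alone. The primary endpoint is not affected, because SAP 8.1 does not use relapse. The correction should be made, since following the stated rules can misclassify eligible subjects in three secondary endpoints.

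**What to change.** 1. **SAP 8.4:** replace the three-answer rule with a table that assigns every Question 7 answer recorded after Day 0, by disease, to relapse, progression or neither. It should cover any later-numbered relapse answer, CML phase change, and progression from stable disease or no response. State a rule for cytogenetic or molecular relapse without hematologic relapse.
2. **SAP 8.5:** define NRM as death without prior relapse or progression, and make the first of relapse or progression, as defined in 8.4, the competing event.
3. **SAP 8.7:** refer to the same definition.
4. If a cause-of-death field is collected, use it to check deaths with no recorded relapse or progression.

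The cost is SAP wording and a revised code mapping. The sponsor needs the Question 7 answer list, and whether a cause-of-death field exists is not shown in the documents. If the three answers already cover every case on the form, the mapping will show this with little work. The downside is that DFS and GRFS may become slightly less favorable and NRM slightly lower.
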